9.3 Subject Withdrawal from Study Medication

If the subject is permanently withdrawn from treatment with study medication, but does not withdraw consent, the investigator must make every effort to have the subject complete all withdrawal assessments at the time of withdrawal, and complete all scheduled follow-up visits. Treatment with study medication must be discontinued if:

- The subject withdraws consent.
- Further participation would be injurious to the subject's health or well-being in the Investigator's medical judgment.

- The study is terminated.
- Marketing approval of CMML
- The subject becomes pregnant
- The subjects exhibits leukemic transformation (as evidenced by bone marrow blast counts of at least 20%, or peripheral blast counts of at least 20% lasting at least 8 weeks.
- No clinical benefit has been attained after 16 weeks of treatment.
- Evidence of Disease progression according to IWG 2006 criteria.
- a subject experiences a DLT.
- a subject is significantly non-compliant with the requirements of the protocol.
- a subject has an adverse experience that would, in the investigator's judgment, make continued participation in the study an unacceptable risk.

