14 MEASUREMENT OF EFFECT

Definitions:

Response and progression will be assessed according to modified International Working Group (IWG) 2006 criteria²³(Appendix B). Improvements must last ≥ 8 weeks.

• Erythroid Response for pretreatment hemoglobin < 11 g/dl:

 \geq 1.5 g/dL increase in hemoglobin.

For transfused subjects having pre-transfusion baseline hemoglobin ≤ 9 g/dL, a reduction of 4 or more RBC units in the previous 8 weeks compared with pretreatment.

 \circ Platelet response for subjects with a pre-treatment platelet count $< 50 \times 10^9 / L$:

Major platelet response: An absolute increase of $\geq 30 \times 10^9$ /L. If platelets are $< 20 \times 10^9$ /L at baseline, then a 100% increase will qualify as a major platelet response. If subjects are transfusion dependent at baseline, platelet transfusion independence sustained for 8 consecutive weeks will qualify as a major platelet response.

Complete platelet response: increase of platelet count to $\geq 100 \times 10^9/L$ for 8 consecutive weeks.

• Neutrophil response with pretreatment ANC $< 1 \times 10^9$ /L:

 \geq 100% increase and an absolute increase of \geq 0.5 x 10⁹/L

Progression/relapse following hematological improvement: At least one of the following:

Any newly developed (RBC/platelet) transfusion dependence,

 \geq 50% decrease from maximum response levels in granulocytes or platelets, or

Reduction of ≥ 1.5 g/dL hemoglobin.

Complete Response (CR)

Bone marrow: \leq 5% myeloblasts with normal maturation of all cell lines Persistent dysplasia will be noted

Peripheral blood:

Hemoglobin $\geq 11 \text{ g/dL}$

Platelets $> 100 \times 10^9 / L$

Neutrophils $\geq 1.0 \times 10^9/L$

BLASTS < 0%

o Partial Response (PR)

All CR criteria if abnormal before treatment, except:

Bone marrow blasts decreased by $\geq 50\%$ over pretreatment but still $\geq 5\%$

Cellularity and morphology not relevant

Marrow Complete Response (mCR)

Bone marrow: $\leq 5\%$ myeloblasts and decrease by $\geq 50\%$ over pretreatment **Peripheral blood: if HI responses, they will be noted in addition to marrow CR**

Stable Disease (SD)
 Failure to achieve at least PR, but no evidence of progression for > 8 weeks
 Duration of Response:

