20 APPENDIX B

RESPONSE CRITERIA FOR SUBJECTS WITH CMML ACCORDING IWG 2006 CRITERIA

ALTERING DISEASE NATURA	AL HISTORY						
Complete remission (CR)	Bone marrow: ≤ 5% myeloblasts with normal maturation of all cell lines						
()	Persistent dysplasia will be noted						
	Peripheral blood:						
	Hemoglobin ≥ 11 g/dL						
	Platelets $\geq 100 \times 10^9 / L$						
	Neutrophils $\geq 1.0 \times 10^9/L$						
	Blasts 0%						
Partial remission (PR)	All CR criteria if abnormal before treatment, except:						
· · · · · ·	Bone marrow blasts decreased by $\geq 50\%$ over pretreatment but still $> 5\%$						
	Cellularity and morphology not relevant						
Marrow CR	Bone marrow: $\leq 5\%$ myeloblasts and decrease by $\geq 50\%$ over pretreatment						
	Peripheral blood: if HI responses, they will be noted in addition to marrow CR						
Stable disease (SD)	Failure to achieve at least PR, but no evidence of progression for > 8 weeks						
Failure	Death during treatment						
	Disease progression characterized by worsening of cytopenias, increase in % of						
	bone marrow blasts, or progression to a more advanced MDS FAB subtype than						
	pretreatment						
Disease Progression (PD)	For subjects with:						
	Less than 5% blasts: $\geq 50\%$ increase in blasts to $\geq 5\%$						
	blasts						
	5%-10% blasts: \geq 50% increase in blasts to \geq 10% blasts						
	10%-20% blasts: \geq 50% increase in blasts to \geq 20%						
	blasts						
	20%-30% blasts: $\geq 50\%$ increase in blasts to $\geq 30\%$						
	blasts						
	Any of the following:						
	At least 50% decrement from maximum						
	remission/response levels in granulocytes or platelets						
	Reduction in hemoglobin (Hgb) concentration by ≥ 2 g/dL						
CHECKENETIC PECPONCE	- Transfusion dependence						
CYTOGENETIC RESPONSE							
Complete	Disappearance of the chromosomal abnormality without appearance of new ones						
Partial At least 50% reduction of the chromosomal abnormality							
HEMATOLOGICAL IMPROVEMENT (HI)							
Erythroid response (HI-E)	Hgb increase by $\geq 1.5 \text{ g/dL}$						
(Pretreatment < 11 g/dL)	Relevant reduction of units of RBC transfusions by an absolute number of at						
	least 4 RBC transfusions/8 weeks compared with the pretreatment transfusion						
	number in the previous 8 weeks. Only RBC transfusions given for a Hgb of ≤						

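### Appendix B scores transfusion dependence as progression with no comparison to baseline, at odds with Section 14; subjects dependent at entry cannot be scored consistently

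*Combined protocol and SAP*

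**What the plan says.** Section 14 states: "Response and progression will be assessed according to modified International Working Group (IWG) 2006 criteria", and points to Appendix B. It has no PD definition of its own, so PD rests on Appendix B.

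In Appendix B, "Transfusion dependence" stands as a bare item under PD in both the response table and the progression/relapse table. It appears again, equally bare, under progression/relapse after HI. Section 14 carries its own list for progression or relapse following HI, and there the item reads "Any newly developed (RBC/platelet) transfusion dependence".

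Subjects who are transfused at entry are expected:

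- Neither 4.1 nor 4.2 excludes them.
- Section 14 gives an erythroid response (HI-E) for transfused subjects: "a reduction of 4 or more RBC units in the previous 8 weeks compared with pretreatment". Appendix B has the same rule: "least 4 RBC transfusions/8 weeks compared with the pretreatment transfusion". Neither requires transfusion independence.
- Section 14 also says: "If subjects are transfusion dependent at baseline, platelet transfusion independence sustained for 8 consecutive weeks will qualify as a major platelet response".

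Two further rules depend on PD. Appendix B defines stable disease (SD) as "Failure to achieve at least PR, but no evidence of progression for > 8 weeks", and Section 3.1.2 counts SD, with HI, CR and PR, in the primary phase 2 endpoint. Section 9.3 lists "Evidence of Disease progression according to IWG 2006 criteria" among the conditions under which study drug must be stopped.

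**The concern.** The other PD items in Appendix B describe a change: a rise in blasts, a fall in granulocytes or platelets from their best level, a drop in hemoglobin. Transfusion dependence as written is a state, and a subject can be in it before the first dose.

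For relapse after HI, Section 14 and Appendix B contradict each other. For PD, nothing in the protocol limits the item to new dependence. Two assessors could therefore score the same subject differently, one applying the appendix as written and the other reading a baseline comparison into it. The difference would reach the SD part of the primary endpoint and a mandatory discontinuation criterion, in a single-arm phase 2 of at most 29 subjects.

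**Working it through.** **Step 1. The texts side by side.**

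| Item | Section 14 | Appendix B |
|---|---|---|
| Relapse after HI | dependence must be newly developed | bare dependence |
| PD | no definition; refers to Appendix B | bare dependence |
| Definition of dependence | none | none |
| Order of HI and PD on the same data | none | none |

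**Step 2. Subjects traced through the literal rules** (red-cell units per 8 weeks; pre-transfusion hemoglobin at or below 9 g/dL).

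- Unchanged, dependent at entry: the bare PD item is met, so SD is not available.
- 4 to 0: reduction 4, HI-E met, no residual need, no conflict.
- 8 to 4, or 12 to 8: reduction 4, HI-E met. If the residual 4 or 8 units still count as dependence, PD is met on the same data.

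So the HI/PD conflict needs baseline use above 4 units per 8 weeks and a residual need that is still called dependence. The SD conflict needs only dependence at entry that persists.

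**Step 3. The stated design reproduced.** Inputs from 15.2: null rate 0.10, alternative 0.30; stop if 1 or fewer of 10 respond; reject the drug if 5 or fewer of 29 respond.

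- Early stopping under the null: 0.9^10 + 10 × 0.1 × 0.9^9 = 0.3487 + 0.3874 = 0.736 (stated 0.74).
- P(declare active) = sum over x = 2 to 10 of Bin(x; 10, p) × P(Bin(19, p) ≥ 6 − x).
- At p = 0.30, for x = 2, 3, 4, 5 and 6 or more: 0.2335 × 0.8668 + 0.2668 × 0.9538 + 0.2001 × 0.9896 + 0.1029 × 0.9989 + 0.0473 = 0.805, so beta is 0.195 (stated 0.19).
- At p = 0.10 the sum is 0.047 (stated 0.05).

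The design figures hold, and this point challenges none of them.

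**Step 4. Illustration.** Let f be the share of true responders scored as progressors instead. The documents give no value for f, so this is an assumption. The scored rate is p = 0.30 × (1 − f).

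| f | scored rate | P(stop at stage 1) | P(declare active) |
|---|---|---|---|
| 0 | 0.30 | 0.149 | 0.81 |
| 0.10 | 0.27 | 0.202 | 0.72 |
| 0.20 | 0.24 | 0.267 | 0.61 |
| 0.30 | 0.21 | 0.346 | 0.48 |
| 0.40 | 0.18 | 0.439 | 0.34 |

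f is not the prevalence of dependence at entry. Dependent subjects who become independent are untouched, so f would be smaller than that prevalence if responses were equally common in both groups.

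**The case against.** The strongest defence is that the literal reading is not the intended one. Every other PD item is a change, the Failure row of Appendix B describes progression as worsening cytopenias, and Section 14 gives subjects dependent at baseline a route to response. A sensible assessor would not call an unchanged entry state progression. As evidence of intent this is fair. It does not remove the problem, because the operative PD row says nothing of the kind and the term is undefined.

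Three stronger conclusions that a reader might draw are not supported:

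- *That PD cancels HI.* Section 3.1.2 joins its components with an or, and the synopsis and 15.1 speak of overall best response. No text says that PD on the same data removes an HI already met, and none says the reverse. Only the SD component is clearly exposed.
- *That duration of response becomes zero.* Section 14 starts that clock at a major or complete platelet response, so a subject with HI-E alone has no duration to lose. It ends the clock, for HI, on the list given earlier in Section 14, which requires new dependence.
- *That every subject dependent at entry is lost to the endpoint and must stop drug at the first assessment.* This needs both the literal reading and a judgment that residual need is dependence. It also ignores subjects who become independent.

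**Conclusion.** The point stands as a contradiction between Section 14 and Appendix B on relapse after HI, together with an unqualified PD item and an undefined term. On the text alone, an unchanged subject dependent at entry cannot be SD, and some HI-E responders are also PD with no rule to choose between the two.

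The documents do not fix the size. The range from 0.81 down to 0.34 holds only for f between 0 and 0.40, with those responders counted as failures. If HI is kept as best response, the loss is smaller and falls mainly on SD. The scoring ambiguity and the conflict over discontinuation remain whatever f is. Because the defect touches the primary endpoint and is cheap to correct, it should be corrected and not left to individual judgment.

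**What to change.** Amend Section 14 and both Appendix B tables together:

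1. Use one wording for the transfusion item in PD and in the relapse rows for endpoint scoring, judged as a change from the pretreatment 8-week transfusion record. Section 14's phrase, "Any newly developed (RBC/platelet) transfusion dependence", is the protocol's own available text.
2. Define transfusion dependence, for red cells and for platelets.
3. Say how worsening of dependence already present at entry is scored. A blanket statement that such subjects never meet PD on transfusion need would hide real deterioration.
4. State whether HI or PD prevails on the same data when best response is assigned.

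PD also feeds the discontinuation list in 9.3, so the sponsor must reconcile that list with the amended scoring. This review does not propose what the stopping rule should be.

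The cost is a wording amendment, with no added visits or subjects. Section 13 requires the 8-week pretreatment transfusion record, and the study calendar has an on-study transfusion log. One detail needs aligning: the opening of Section 13 makes the record compulsory, while the 13.1 list asks for it only where available. The comparator should be required, or the handling of a missing record stated.

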1 OBJECTIVES

- 1.1 Primary Objective:
- 1.1.1 To evaluate the safety and tolerability of ruxolitinib in CMML subjects at diagnosis or relapse.
- 1.1.2 To determine overall response rates as measured by the international working group criteria (2006).
- 1.2 Secondary Objectives:
- 1.2.1 To determine the time to AML transformation of subjects on Ruxolitinib.
- 1.2.2 To determine the median overall survival.
- 1.2.3 To determine the duration of response achieved as in secondary endpoint one.
- 1.2.4 To determine the change in symptom score from baseline to best response.
- 1.2.5 To determine the change in spleen length at 16 weeks
- 1.2.6 To determine the change in downstream targets of JAK2 on ruxolitinib.
- 1.2.7 To determine if the *in vitro* activity of ruxolitinib correlates to response rates.
- 1.2.8 To determine if a correlation exist between the presence of the known recurrent mutations (JAK2, c-CBL, N-RAS, K-RAS, RUNX-1, TET2, SRSF2, EZH2, ASXL1, and DNMT3a) and response to ruxolitinib. .
- 1.2.9 To determine non-V617F JAK2 mutations at end of study or progression and their clinical relevance in the context of ruxolitinib.

We recognize that this is a small study and the secondary objectives are of exploratory nature.

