3 STUDY ENDPOINTS

3.1 Primary

- 3.1.1 The maximum tolerated dose (MTD) of ruxolitinib for the treatment of CMML. The MTD is defined as the highest dose where less than 33% of subjects experience a drug related predefined dose limited toxicity (DLT).
- 3.1.2 Proportion of subject achieving clinical benefit defined as hematologic improvement, complete remission, partial remission, or stable disease by the IWG 2006 criteria (see appendix B)

- 3.2 Secondary
- **3.2.1** Acute myeloid leukemia (AML) transformation according to WHO criteria.
- **3.2.2** Overall survival (OS).
- **3.2.3** Duration of response.
- 3.2.4 The Myeloproliferative Neoplasms Symptom Assessment Form (MPN-SAF) at baseline and at best response.
- 3.2.5 >50% decrease in splenic length as measured by physical exam if applicable
- **3.2.6** The suppression of pSTAT5 intracellular signaling after ruxolitinib in CMML subjects (pretreatment, at 1-2hr post treatment, cycle 2, cycle 4, and progression.)
- **3.2.7** Determine number of colonies formed in the presence of GM-CSF and/or ruxolitinib (pretreatment and progression) as a future predictor of response.
- 3.2.8 Mutational status in our CMML subjects by sanger sequencing of JAK2, c-CBL, N-RAS, K-RAS,RUNX-1, TET2, SRSF2, EZH2, ASXL1, and DNMT3a (pretreatment and progression).
- 3.2.9 Mutational status of JAK2 tyrosine kinase at time of progression by deep sequencing of JAK2 to include M929I, Y931C, G935R, R938L, I960V, E985K. (pretreatment and at progression)

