10 DOSING DELAYS/MODIFICATIONS

All subjects enrolled in the phase 1 portion will start treatment on the assigned dose per cohort based on the dose escalation algorithm provided. No dose delays or modifications are allowed during this period. All subjects enrolled in the phase 2 portion may have the following dose delays/modifications once the MTD has been defined.

Ruxolitinib may be held by the Investigator at any time if there is concern about subject safety. Dosing must be halted immediately if either of the following occurs:

- Platelet counts fall below 10,000/μL and/or a life-threatening bleeding event
- Febrile neutropenia

Dosing may be reinstated following dose interruption using the re-start schema detailed in below.

10.1 Dose Adjustments.

In order to provide sufficient data to make the dose adjustment decisions, it is recommended that hematology parameters be obtained weekly and at least two times weekly for platelet count $< 25,000/\mu L$ or ANC $< 500/\mu L$. In the event that any subject permanently discontinues the study drug, regardless of reason, reasonable efforts should be made to have the subject return for an early termination visit. If the drug discontinuation is being contemplated for a reason other than low platelet count or

low ANC, the use of a tapering strategy should be considered (see below). The date the subject discontinued the study drug and the specific reason for discontinuation will be recorded in the eCRF; eg, reasons such as discontinued due to inadequate efficacy or withdrawn due to adverse event. This information will be used to summarize the reasons for study discontinuation. Efforts will be made to follow subjects who discontinue from the study in order to determine overall survival and leukemia free survival. Investigators will contact subjects every 6 months to determine if subjects have undergone leukemic transformation, or death, and for the latter, the cause of death.

10.2 Dose Adjustments in Ruxolitinib Tablets for Safety.

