15.6 Analyses of Secondary Endpoints

Analyses of the following secondary endpoints will be performed as well:

- 15.6.1 Acute myeloid leukemia (AML) transformation according to WHO criteria.
- **15.6.2** Overall survival (OS).
- **15.6.3** Duration of response.
- 15.6.4 The Myeloproliferative Neoplasms Symptom Assessment Form (MPN-SAF) at baseline and at best response.
- 15.6.5 >50% decrease in splenic length as measured by physical exam if applicable
- **15.6.6** The suppression of pSTAT5 intracellular signaling after ruxolitinib in CMML subjects (pretreatment, at 1-2hr post treatment, cycle 2, cycle 4, and progression.)
- **15.6.7** Determine number of colonies formed in the presence of GM-CSF and/or ruxolitinib (pretreatment and progression) as a future predictor of response.
- **15.6.8** Mutational status in our CMML subjects by sanger sequencing of JAK2, c-CBL, N-RAS, K-RAS,RUNX-1, TET2, SRSF2, EZH2, ASXL1, and DNMT3a (pretreatment and progression).
- **15.6.9** Mutational status of JAK2 tyrosine kinase at time of progression by deep sequencing of JAK2 to include M929I, Y931C, G935R, R938L, I960V, E985K.

(pretreatment and at progression)

We recognize that this is mainly a phase I study with an extension phase at the MTD. However, preliminary data on the above endpoints will prove to be very useful for further investigation of this protocol's treatment. Such data will be summarized appropriately focusing mostly on the subjects treated at the MTD dose in an exploratory fashion. Both point estimates and 95% confidence intervals will be reported, if feasible. Time-to-event endpoints such as OS will be summarized using the Kaplan-Meier product-limit method.

16 Laboratory Correlates

Unless otherwise specified, all laboratory correlates will be performed in the laboratory of [name] under the direction of Drs [name] and [name].

H.LEE MOFFITT CANCER CENTER

CC: [name]

STABILE RESEARCH BUILDING

SRB-2

[name]

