District magnency (III D)	9.0 g/dL pretreatment will count in the RBC transfusion evaluation Platelet response (HI-P) Absolute increase of $\geq 30 \times 10^9$ /L for subjects starting with $\geq 20 \times 10^9$ /L						
Platelet response (HI-P) (Pretreatment < 100 x 10 ⁹ /L)	Absolute increase of $\ge 30 \times 10^{7}$ L for subjects starting with $\ge 20 \times 10^{7}$ L Increase from $< 20 \times 10^{9}$ /L to $\ge 20 \times 10^{9}$ /L and by at least 100%						
	At least 100% increase and an absolute increase of > 0.5 x 10 ⁹ /L						
Neutrophil response (HI-N)	At least 100% increase and an absolute increase of > 0.5 x 10 /L						
(Pretreatment $< 1.0 \times 10^9/L$)							

PROGRESSION/RELAPSE CRITERIA FOR SUBJECTS WITH CMML

ALTERING DISEASE NAT	URAL HISTORY					
Disease Progression (PD)	For subjects with:					
	Less than 5% blasts: \geq 50% increase in blasts to $>$					
	5% blasts					
	5%-10% blasts: \geq 50% increase in blasts to \geq 10%					
	blasts					
	10%-20% blasts: \geq 50% increase in blasts to \geq 20%					
	blasts					
	20%-30% blasts: \geq 50% increase in blasts to \geq 30%					
	blasts					
	Any of the following:					
	At least 50% decrement from maximum					
	remission/response levels in granulocytes or					
	platelets					
	Reduction in hemoglobin (Hgb) concentration by ≥					
	2 g/dL					
Disease transformation	Transfusion dependence					
	Transformation to AML (30% or more blasts)					
Relapse after CR or PR	At least one of the following:					
	Return to pretreatment bone marrow blast % Decrement of ≥ 50% from maximum					
	remission/response levels in granulocytes or					
	platelets					
	- Reduction in Hgb concentration by ≥ 1.5 g/dL or transfusion					
	dependence					
HEMATOLOGICAL IMPR						
Progression/relapse after HI	At least one of the following:					
	At least 50% decrement from maximum response					
	levels in granulocytes or platelets					
	Reduction in Hgb by $\geq 1.5 \text{ g/dL}$					
	- Transfusion dependence					

21 APPENDIX C: CYP3A4 Strong Inhibitors

HIV Antivirals:

- -indinavir
- -boceprevir
- -lopinavir/ritonavir
- -ritonavir
- -telaprevir
- -nelfinavir
- -saquinavir

Others:

- -clarithromycin
- -conivaptan
- -grapefruit juice
- -mibefradil
- -posaconazole
- -voriconazole
- -itraconazole
- -ketoconazole
- -nefazodone
- -telithromycin

^{*} Dose reductions as in section 7 are required for strong inhibitors of the CYP3A4.

22 APPENDIX D: Myeloproliferative Neoplasms-Symptom Assesment Form (MPN-SAF)

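### The AML-transformation endpoint has no stated blast cut-off, 9.3 and Appendix B put different numbers on transformation, and 15.6 has no rule for death before AML (minor)

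*Combined protocol and SAP*

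**What the plan says.** Section 1.2.1 sets the objective: "To determine the time to AML transformation of subjects on Ruxolitinib". Sections 3.2.1 and 15.6.1 give the matching endpoint as "Acute myeloid leukemia (AML) transformation according to WHO criteria", with no blast percentage. Appendix E, the only WHO table in the document, classifies CMML-1 and CMML-2. It caps CMML-2 below 19% blasts and does not mention AML.

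Two places put a number on transformation. Section 9.3 lists leukemic transformation among the reasons to stop study drug, evidenced by "bone marrow blast counts of at least 20%, or peripheral blast counts of at least 20% lasting at least 8 weeks". The progression/relapse table in Appendix B has "Transformation to AML (30% or more blasts", with no compartment and no persistence condition. The same table keeps a 20%-30% blast band under disease progression.

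On analysis, section 15.6 says "Time-to-event endpoints such as OS will be summarized using the Kaplan-Meier product-limit method". Section 10.1 says discontinued subjects will be followed "in order to determine overall survival and leukemia free survival", with contact every six months to "determine if subjects have undergone leukemic transformation, or death, and for the latter, the cause of death". Leukemia-free survival is not defined there and does not appear in 3.2 or 15.6. Section 13.6 collects vital status, date of death, AML status and AML date off study for two years. On the weight of these endpoints, section 1.2 adds "We recognize that this is a small study and the secondary objectives are of exploratory nature".

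**The concern.** There are two separate gaps.

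**Definition.** Whether a subject at 20-29% marrow blasts counts as an AML event, and on what date, depends on a cut-off that the endpoint does not state. The numbers elsewhere in the protocol point in different directions. Section 13.6 does not list the blast percentage among the off-study items, so a later reclassification could be difficult.

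**Estimator.** Section 2.1 puts median survival in this disease at 12 to 20 months, so many subjects may die without AML within the two-year follow-up. A Kaplan-Meier curve for time to AML then needs a stated rule for those deaths. If they are treated as censored, one minus Kaplan-Meier estimates AML risk as if death could not intervene, and it exceeds the proportion who actually develop AML. If they are counted as events, the quantity is leukemia-free survival, which Kaplan-Meier estimates properly but which is not time to AML. The reported figure would depend on a choice that the plan does not make.

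**Working it through.** **Definition, passages side by side**

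| Place | Role | Transformation |
|---|---|---|
| 3.2.1, 15.6.1 | Endpoint | WHO criteria, no number |
| Appendix E | WHO classification of CMML | CMML-2 below 19%; no AML limit |
| 9.3 | Treatment withdrawal | Marrow at least 20%, or peripheral at least 20% lasting at least 8 weeks |
| Appendix B | IWG response/progression | 30% or more |

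In 9.3 the 8-week condition most naturally attaches to peripheral blasts only. On that reading, a subject with 20-29% marrow blasts is transformed under 9.3 and not under Appendix B. The 30% does not look like a slip, because the 20%-30% progression band in the same table fits it. With 29 subjects, each one reclassified moves the crude AML proportion by 1/29 = 3.4 points. Nothing in the documents says how many would fall in that range.

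**Estimator, size of the effect if deaths were censored**

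From the documents: median OS of 12 to 20 months (2.1), two years of off-study follow-up (13.6) and 29 phase 2 subjects (15.2).

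Assumed, because the documents give no figure: constant hazards; AML hazard λ = 0.05, 0.10 or 0.20 per year; median survival after AML of 3, 6 or 12 months, giving post-AML hazard μ = ln 2 / (that median in years). The hazard d of death without AML is solved so that median OS equals m = 12, 16 or 20 months (in years in the formula):

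exp(−(λ+d)m) + λ[exp(−μm) − exp(−(λ+d)m)] / ((λ+d) − μ) = 0.5

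This gives 27 cases. At 24 months:

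- 1 − KM = 1 − exp(−2λ) = 9.5%, 18.1% or 33.0%
- Cumulative incidence (CIF) = λ/(λ+d) × [1 − exp(−2(λ+d))]
- Death without AML = d/(λ+d) × [1 − exp(−2(λ+d))]

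Middle case (λ = 0.10, OS 16 months, post-AML 6 months): d = 0.479, so CIF = 0.10/0.579 × [1 − exp(−1.158)] = 11.8%. Against 18.1%, the gap is 6.3 points, or 1.8 of 29 subjects. Expected AML events are 29 × 0.1185 = 3.4.

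| λ per year | 1 − KM | Smallest gap (OS 20, post-AML 3) | Middle gap (OS 16, post-AML 6) | Largest gap (OS 12, post-AML 12) |
|---|---|---|---|---|
| 0.05 | 9.5% | 2.8 | 3.4 | 4.3 |
| 0.10 | 18.1% | 4.8 | 6.3 | 8.1 |
| 0.20 | 33.0% | 6.9 | 10.4 | 14.3 |

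Gaps are in percentage points. Death without AML by 24 months runs from 34% to 72% across the 27 cases.

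For comparison with sampling error, the approximate 95% half-width is 1.96 × √(CIF(1 − CIF)/n). At n = 29 it runs from 8.1 to 16.0 points. The gap exceeds it in one case of 27 (λ = 0.20, OS 12, post-AML 12: 14.3 against 14.2).

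Section 15.6 focuses mostly on subjects treated at the MTD, so n is not fixed at 29. It could be 10 from phase 2 if stage 1 stops the trial, or about 29 + 6 = 35 if a phase 1 cohort at the MTD is added. The gap exceeds the half-width in 0 of 27 cases at n = 10 and in 2 of 27 at n = 35.

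**The case against.** The strongest reply is that the endpoint does have a governing standard. Every endpoint list says WHO criteria. Section 14 assigns Appendix B to response and progression, and 9.3 is a withdrawal rule, so neither was written to define this endpoint. That stands. A reader might infer from the conflict that the AML definition is left entirely open, and the documents do not support that. What is missing is the number behind the named standard, and what conflicts is two numbers elsewhere for the same event.

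It can also be said that Appendix E points to a limit, because a subject at 20-29% no longer fits its CMML-2 row. That is a fair inference about direction, but Appendix E states no AML threshold and does not settle the number.

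On the estimator, a reader might infer that the plan will censor deaths before AML and so report a biased estimate. The plan does not say that. Section 15.6 is silent, and the mention of leukemia-free survival in 10.1, with both transformation and death followed, would fit a valid use of Kaplan-Meier. The defect is a missing rule, and the overstatement is conditional. Defining leukemia-free survival would give Kaplan-Meier a proper use, but would not by itself answer the objective in 1.2.1, which is time to AML.

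Finally, the gap sizes rest on assumed hazards and mostly lie within sampling error. That also stands and limits the severity. It does not remove the point, because under censoring the error runs in one direction and a confidence interval would be centred on the wrong quantity.

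**Conclusion.** The point holds at minor severity. The text conflict between 9.3 and Appendix B is plain, and no section gives the blast cut-off for the endpoint. Section 15.6 offers only Kaplan-Meier for an objective in which death competes with the event, without a rule for those deaths. If they were censored, AML incidence at 24 months would be overstated by about 3 to 14 points. That range rests on constant hazards, the assumed AML rates and post-AML survival, and the median OS quoted in section 2.1. It is usually smaller than the sampling uncertainty with 10 to 35 subjects. The primary endpoints, the Simon two-stage rules and the sample size are unaffected.

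**What to change.** In 3.2.1 and 15.6.1, state the single AML definition that applies to the endpoint (blast cut-off, compartment and any persistence condition) and the date that counts as the event. Reconcile 9.3 and Appendix B with it, or say explicitly that they serve other purposes and why their numbers differ. Which cut-off applies, in the endpoint or in the withdrawal rule, is for the sponsor to decide.

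In 15.6, estimate time to AML by the cumulative incidence function with death without AML as a competing event, and give a 95% confidence interval. Keep Kaplan-Meier for OS and, if reported, for leukemia-free survival defined as AML or death.

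The cost is a few lines of text and a standard routine. The dates needed are already collected under 13.6. The blast percentage may need to be recorded when AML is reported off study.
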